5.0 Study Design and Statistical Analysis Plan

5.1 *Describe the basic study design/approach (e.g., qualitative study using five focus groups of first year students to describe assimilation into the university community; randomized controlled trial of a behavioral change intervention to increase dietary intake of whole grains; pre- post-test evaluation of new pedagogical techniques to improve adult literacy):*

For our primary objective, a one-group repeated-measures design will be used to validate the use of wearable sensors to capture responses to LOBs. Subjects will use wearable sensors for three weeks to capture responses to naturally-occurring trips and slips during daily life. Subjects will then complete a laboratory session to capture lab-induced LOB responses simultaneously from the wearable sensors and a gold-standard optoelectronic motion capture system.

For our secondary objective, a three-group posttest-only design will be used to compare the effects of three balance training exercises on responses to LOBs after laboratory-induced trips and slips, and two weeks of naturally-occurring real-world trips and slips. Subjects will first complete three weeks of their assigned training. Subjects will then

21-1072 Validation and application of wearable sensors for capturing responses to losses of balance

complete a laboratory session to capture lab-induced LOB responses simultaneously from the wearable sensors and a gold-standard optoelectronic motion capture system. Subjects will then use wearable sensors for two weeks to capture responses to naturally-occurring trips and slips during daily life.

5.2 Describe corresponding data analysis plan/approach (e.g., content analysis of focus group transcripts; descriptive analysis followed by linear regression modeling; nonparametric analysis of pre- and post-test measures):

Hypothesis 1: LOB response measures obtained from the wearable sensors after lab-induced trips and slips will exhibit statistical agreement with the same measures simultaneously obtained from a gold-standard laboratory-based motion capture system.

To address Hypothesis 1, a Bland-Altman analysis will be used to evaluate level of agreement between the two systems. This approach will reveal any measurement bias between the two systems, and provide bounds for these differences.

Hypothesis 2: Real-world LOB responses will show greater variety than laboratory-induced LOB responses.

To address Hypothesis 2, a repeated-measures ANOVA (with a random effect for subject) will first be used to compare means of key kinematic measures of LOB responses between environments (real-world vs lab). Second, we will compare statistical variability by examining the model residuals between real-world and lab environments using hypothesis testing (essentially Levene's test) and interval estimation to quantify potential differences in variability.

Hypothesis 3: NT and TT participants will exhibit improved LOB responses after lab-induced trips and slips compared to ST participants.

To address Hypothesis 3, response variables will be compared between NT, TT, and ST participants using a one-way ANOVA with group as the independent variable and covariates included as needed. A significant effect of group will be followed by post-hoc analysis using Dunnett's test to determine whether NT, TT, or both differ from ST.

Hypothesis 4: NT and TT participants will exhibit statistically-equivalent LOB responses after lab-induced trips and slips.

To address Hypothesis 4, agreement of response variables between NT and TT participants will be evaluated using statistical equivalence test.

A comparison between the three balance training exercises on LOB responses after any naturally-occurring real-world trips will be done qualitatively and thus not have an explicit hypotheses to be tested.

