2.0 Objectives

2.1 Describe the purpose, specific aims, or objectives of this study:

The primary objective is to validate the use of wearable sensors for capturing responses to losses of balance (LOBs). During laboratory testing, we will use wearable sensors and a laboratory-based optoelectronic motion capture system to simultaneously measure responses to LOBs after laboratory-induced trips and slips. During real-world testing, we will use wearable sensors to measure responses to LOBs after any naturally-occurring trips or slips during the real-world daily lives of participants.

The secondary objective of this study is to compare the effects of three balance training exercises on responses to LOBs measured in the laboratory and in the real-world during daily life.

2.2 State the hypotheses to be tested:

Hypotheses for our primary objective that will involve non-balance training participants:

Hypothesis 1: LOB response measures obtained from the wearable sensors after lab-induced trips and slips will exhibit statistical agreement with the same measures obtained simultaneously from a laboratory-based optoelectronic motion capture system.

Hypothesis 2: Real-world LOB responses will show greater variety than laboratory-induced LOB responses.

Hypotheses for our secondary objective that will involve balance training participants:

Hypothesis 3: NT and TT participants will exhibit improved LOB responses after lab-induced trips and slips compared to ST participants.

Hypothesis 4: NT and TT participants will exhibit statistically-equivalent LOB responses after lab-induced trips and slips.

Hypothesis 5: NT and TT participants will exhibit improved LOB responses after any naturally-occurring real-world trips and slips.

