8.0 Procedures Involved

8.1 Describe and explain the study design:

For our primary objective, a one-group repeated-measures design will be used to validate the use of wearable sensors to capture responses to LOBs. Non-balance training participants will use wearable sensors for three weeks to capture responses to naturally-occurring trips and slips during daily life. Subjects will then complete a laboratory session to capture lab-induced LOB responses simultaneously from the wearable sensors and a gold-standard optoelectronic motion capture system.

For our secondary objective, a three-group posttest-only design will be used to compare the effects of three balance training exercises on responses to LOBs after laboratory-induced trips and slips, and two weeks of naturally-occurring real-world trips and slips. Balance training participants will first complete three weeks of their assigned training. Subjects will then complete a laboratory session to capture lab-induced LOB responses simultaneously from the wearable sensors and a gold-standard optoelectronic motion capture system. Subjects will then use wearable sensors for two weeks to capture responses to naturally-occurring trips and slips during daily life.

8.2 Provide a description of:

- *All research procedures being performed*
- *If the study has more than one procedure, session, and/or subject population, describe each procedure, session, and/or study*

population separately. For complex studies, you are encouraged to include a figure or chart.

Recruitment and Informed Consent

- Interested participants will respond to our recruitment strategies and contact the investigators.
- The investigators will telephone interested participants and follow the telephone script included in the application to first screen participants for inclusion criteria. If participants satisfy the inclusion criteria, the investigator will continue the telephone conversation and administer the health questionnaire described in an attachment to this application. De-identified information from this health questionnaire will then be reviewed by a health professional with specialist training for the geriatric population. This specialist will be a board certified physician or board certified specialist in geriatric physical therapy.

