21-1072 Validation and application of wearable sensors for capturing responses to losses of balance

weights and using more challenging balance postures. The progression of difficulty will be based on the investigators perception of the improving ability of the participant.

- If the participant is assigned no training, then no such training will be performed.
- All participants will then complete the two types of LOB response measurements described below.

Measure LOB responses in the laboratory:

- Each participant will complete a lab session to assess their response to an LOB after lab-induced trips and slips. This session will take place in our research lab on the VT campus ([name]). During these sessions, participants will wear a safety harness supported overhead to prevent impact with the floor in the event of an unsuccessful balance recovery. First, the appropriate size will be selected from a range of sizes we have in the lab. Second, the investigator will assist the participant in donning the harness, securing all straps and connections, and inspecting and confirming the overall fit. The PI ([name]) has extensive experience with the harnesses, and will train the student investigators in their use.
- Participants will also wear reflective markers so researchers can measure their movements with a laboratory motion capture system. As we have done for years, these markers will be affixed to clothing and skin at selected anatomical landmarks using double-sided tape. [name] will place markers on participants. Markers will be placed bilaterally on the shoes at the toes and heels, ankles, knees, hips, shoulders, elbows, wrists, and on a headband worn around the head.

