Data collected during the laboratory testing session will include body motion during trip and slip LOB responses obtained simultaneously from two systems. The first system is the wearable sensors (<https://apdm.com/wearable-sensors/>) with individual sensors worn on each foot and one on the sternum using a shoulder strap under the clothing. The second system is the lab-based optoelectronic motion capture system (Qualisys, Inc) and reflective markers (small balls approximately 1 cm in diameter) placed at specific locations on the body. Data from these systems will be recorded as a computer file on a password-protected and VT-managed computer. In these files, participants will only be identified by a numeric code, and not personally-identifiable information will be recorded.

Video recordings and photographs of participants during perturbations will be obtained to assist with data analysis and for possible use in presentations. Participants will need to provide permission, on the Informed Consent Form, for us to use these in presentations. These videos and photos will be kept on a password-protected and VT-managed computer.

Data from the wearable sensors during real-world LOB response tracking will be automatically stored onboard the sensors themselves until downloaded by the study

21-1072 Validation and application of wearable sensors for capturing responses to losses of balance

team when returned to the study team after the two or three week data collection. Participants will be asked to charge the sensors nightly, and will be given the charger and detailed instructions and training on how to do that from the study team. When downloaded by the study team, the data file is in the form of a de-identified Excel file that is ready for analysis, and these files will be kept on a password-protected and VT-managed computer.

Data will be collected by the voice recorder by having participants press a record button on it, having participants speak into the recorder the information requested by the study team, and then pressing a button to stop. These recordings include a time/date stamp, and will be downloaded for analysis by the study team when returned to the study team. These files will be kept on a password-protected and VT-managed computer.

8.5 Who will transcribe or code audio and/or video recordings?:

[name] will transcribe voice recordings. No other transcriptions will be performed.

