14.0 Number of Subjects

14.1 Indicate the total number of subjects to be enrolled and how this number was determined (e.g., sample size calculation [show], number of available subjects in a finite pool, number of tests funding award would allow):

60 participants will be enrolled. This number is based upon a formal sample size analysis described here:

30 non-balance training participants will be recruited for our primary objective. Given that this objective is for validation, no formal effect sizes could be determined. Rather, we estimated 30 participants for this objective to be a reasonable number based upon our available resources and the number of expected LOBs estimated from prior work [Handelzalts et al. 2020].

30 balance training participants will be recruited for our secondary objective and be based upon Hypothesis 3: NT and TT participants will exhibit improved LOB responses after lab-induced trips and slips compared to ST participants.

The sample size was determined using data from lab-induced trips among community-dwelling older adults aged 65 years or older (Pavol et al., 2001). The effect size index (i.e., Cohen's $d = 1.45$) was determined using the difference in mean trunk angle from vertical at the time of recovery foot ground contact between fallers and non-fallers (17.4°) and the combined standard deviation (12°). The difference in means was considered the minimal clinically important difference based on the anchor-based method (Rai et al., 2015). Using G*Power (Faul et al., 2007) for an independent t-test with 80% power and a one-sided Type I error (or alpha) of 5%, a sample size of seven participants per group is needed. In an effort to be conservative and account for any participants withdrawing from the study, 10 participants per balance training group (TT,NT,ST) will be recruited.

Handelzalts, S., N.B. Alexander, N. Mastruserio, L.V. Nyquist, D.M. Strasburg, and L.V. Ojeda. Detection of Real-World Trips in At-Fall Risk Community Dwelling Older Adults Using Wearable Sensors. *Front Med*, 2020. 7: p. 514.

14.2 If this is a multi-site study, indicate the number of subjects to be enrolled at this site and the total to be enrolled from all sites:

21-1072 Validation and application of wearable sensors for capturing responses to losses of balance

Not a multi-site study.

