14.3 If applicable, indicate the number of potential subjects you expect to screen for enrollment, and the number of subjects you will need to complete the research procedures:

N/A

14.4 If the study has more than one procedure, indicate the total number of subjects to undergo each procedure separately:

30 participants will be assigned to be non-balance training participants

30 participants will be assigned to be balance training participants, with 10 completing each of the three types of training under investigation (TT, NT, ST).

Other than these differences in balance training, all other testing will be the same for all participants.

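### The primary sensor-validation analysis (Hypothesis 1) is assigned to 30 participants although all 60 are recorded by both systems; using all 60 would cut the uncertainty of each limit of agreement by about 30%

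*Combined protocol and SAP*

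**What the plan says.** Section 2.2 introduces Hypotheses 1 and 2 under the line "Hypotheses for our primary objective that will involve non-balance training participants". The Study Summary (section 1.0) likewise uses the non-balance training label for the participants of the primary objective. Section 14.1 recruits 30 of them and explains the number this way: "we estimated 30 participants for this objective to be a reasonable number based upon our available resources", together with the number of LOBs expected from prior work. It states no target precision. The Hypothesis 1 text in section 5.2 says that "a Bland-Altman analysis will be used to evaluate level of agreement between the two systems". It promises a bias and bounds for the differences and names no population of its own.

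The data collection is wider than that. Sections 5.1 and 8.1 say of the non-training cohort, and again of the training cohort, that the laboratory session will "capture lab-induced LOB responses simultaneously from the wearable sensors and a gold-standard optoelectronic motion capture system". Section 8.2 says that "All participants will then complete the two types of LOB response measurements described below", one of the two being the laboratory session. Section 8.4 adds, without restriction to a cohort: "Data collected during the laboratory testing session will include body motion during trip and slip LOB responses obtained simultaneously from two systems". Section 14.4 closes the matter: "Other than these differences in balance training, all other testing will be the same for all participants".

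**The concern.** Hypothesis 1 asks how far the wearable sensors differ from the reference system when both record the same event. Every participant who completes the laboratory session supplies such pairs, so 60 people produce the data and the plan assigns 30 of them to the analysis. The documents give no reason for leaving the other 30 out.

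What is at stake is precision. A limit of agreement depends on an estimated SD and is uncertain in a small sample. With 30 participants, each bound that the plan promises is known less well than the collected data allow. This is the primary objective, and the missing half of the pairs will already have been paid for.

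**Working it through.** **The plan's own figures.** The 30 for Hypothesis 1 has no calculation to reproduce. The only calculated figure is for Hypothesis 3 in section 14.1: d = 17.4/12 = 1.45, one-sided 5%, 80% power, where "a sample size of seven participants per group is needed". A noncentral t calculation gives 75.5% power at 6 per group and 81.9% at 7, so it reproduces. It bears on Hypothesis 1 only in showing that the authors count participants, not events.

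**Inputs.** n = 30 (sections 2.2 and 14.1) and n = 60 (sections 8.2, 14.1 and 14.4). SD below means the SD of a single sensor-minus-camera difference. The number of events per participant is not stated, so other event counts and their within-person correlations are assumptions.

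**One event per participant.** The standard error of a limit, in SD units, is sqrt(1/n + 1.96²/(2(n−1))).

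- n = 30: sqrt(0.0333 + 0.0662) = 0.3155; 95% half-width 1.96 × 0.3155 = 0.618.
- n = 60: sqrt(0.0167 + 0.0326) = 0.2219; 95% half-width 1.96 × 0.2219 = 0.435.
- Reduction: 1 − 0.2219/0.3155 = 29.7%. Simulation gave 0.616 and 0.434.

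With t quantiles the half-widths are 0.645 and 0.444, a reduction of 31.2%.

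**Several events per participant.** The limits now use between- plus within-participant variance. Simulated half-widths at assumed correlations of 0.2, 0.3 and 0.5:

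| Events each | 30 participants | 60 participants |
|---|---|---|
| 2 | 0.46, 0.47, 0.50 | 0.32, 0.33, 0.35 |
| 3 | 0.39, 0.41, 0.46 | 0.27, 0.29, 0.32 |
| 6 | 0.30, 0.34, 0.41 | 0.21, 0.24, 0.29 |

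The reduction is 29 to 30% in every cell. It is essentially 1 − 1/sqrt(2) = 29.3%, the gain from doubling the participants. It compares the same method at both sizes, so none of it is owed to the repeated-measurement formula.

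**Withdrawals.** Keep 30 as the comparator and let the total fall to 57, 54 or 51. The t-based reduction is 29%, 27% or 25%. With the normal quantile (standard errors 0.2277, 0.2340 and 0.2409 against 0.3155) it is 28%, 26% or 24%.

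**What the gain assumes.** The figures above treat the bias as common to both cohorts. If each cohort keeps its own bias and only the SD is pooled (58 degrees of freedom), the standard error of the non-training limit is sqrt(1/30 + 1.96²/(2 × 58)) = sqrt(0.0333 + 0.0331) = 0.258. The reduction is then 1 − 0.258/0.3155 = 18%.

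**Can the data test that assumption?** With one event each and equal SDs, the difference in bias between two cohorts of 30 has standard error sqrt(2/30) = 0.258 SD and a 95% half-width of about 0.5 SD. A true difference of 0.38 SD would be detected with about 30% power. Ignored, it would shift the pooled upper limit away from the non-training limit by 0.38/2 + 1.96 × (sqrt(1 + 0.38²/4) − 1) = 0.19 + 0.035 = 0.225 SD. The root mean square error is then sqrt(0.225² + 0.222²) = 0.316, no better than the 0.3155 from 30 participants alone. At 0.5 SD, pooling is worse: about 0.38.

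**The case against.** The strongest reply is that the 30 are a deliberate population. The primary objective has its own one-group design and its own cohort. Trained participants are expected to respond differently to a perturbation, and the order of events differs: non-training participants wear the sensors in daily life before the laboratory session, training participants after it. Pooling could therefore mix two levels of agreement, and setting 60 beside an overlapping 30 does not test for that. This stands as a caution. It is why the fix needs a cohort term and why the 30-only result must remain. It does not justify leaving the other 30 out altogether, because the documents give no reason to expect sensor error to depend on cohort.

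It can also be said that section 2.2 does not say only, that no agreement criterion is set which extra precision would decide, and that the plan promises limits without mentioning confidence intervals around them. All true. They make this an improvement to the plan, not a defect that invalidates Hypothesis 1.

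Two stronger readings are tempting. A reader might infer that repeated events will make the limits too narrow. Uncorrected participant means would make them 13 to 42% too narrow for a single event (assumed 2 to 6 events, correlation 0.2 to 0.5), but the plan never proposes averaging, and simply pooling events leaves the limits at about 99% of their correct width. A reader might also infer that the one-way ANOVA for Hypothesis 3 will treat correlated events as independent rows and inflate its error rate. Section 14.1 sizes that comparison in participants, event rows are not a stated plan, and with one value per participant the problem does not arise.

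**Conclusion.** The point holds as a matter of efficiency in the primary analysis. The plan assigns Hypothesis 1 to 30 participants while collecting the same paired recordings in 60. Using all 60 would reduce the 95% uncertainty around each limit by about 30% if everyone completes, and by about 25 to 29% with 51 to 57 completers. The percentage does not depend on the assumed event counts or correlations. It does depend on a common bias and spread in the two cohorts; with separate biases the gain for the non-training limit is about 18%.

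Nothing here shows that 30 participants are too few or that a Hypothesis 1 conclusion would change, since no precision target or agreement bound is stated. The number of events per participant and the unit of analysis for Hypotheses 3 and 4 deserve a clarifying sentence, but they are not part of this conclusion.

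**What to change.** In section 5.2, under Hypothesis 1, and consistently in sections 1.0, 2.2 and 14.1:

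- Estimate bias and limits of agreement in all 60 participants, using limits for repeated measurements (between- plus within-participant variance) with participant-level confidence intervals.
- Include cohort (non-training versus training) as a term, and report its estimated effect on bias with a confidence interval. Do not treat a non-significant result as evidence of no difference.
- Report the limits in the 30 non-training participants alone beside the 60-participant result.

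The cost is SAP wording and a little more analysis, with no added participants, visits or measurements. The downside is the pooling assumption: sensor-minus-camera differences must not depend on training or on whether daily wear came before or after the laboratory session. A comparison of 30 with 30 has limited power to detect a modest departure, so the 30-only limits should stay in the report whatever the cohort estimate shows.

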- Participants will first complete a minimum of 10 walking trials along a 12-meter-long walkway at a self-selected speed. Instructions will be to “walk as if you have somewhere to go, and if tripped or slipped, recover your balance and continue walking.” All participants will wear the same model of rubber-soled shoes and a safety harness affixed to a ceiling-mounted track that spans the length of the walkway. After initial walking trials, trips and slips will be induced during randomly-selected trials with walking trials and rest breaks interspersed. As in our prior work, trips will be induced using a tripping obstacle that is initially concealed and level with the walkway. Upon proper placement of the foot relative to the obstacle while walking, the obstacle will be activated and quickly rise and result in a trip shortly after mid-swing. In an effort to add variety to the LOB responses, three trip obstacle heights from prior tripping studies will be used including 5, 7.5, and 10 cm. Slips will be induced using the same methods and distraction efforts as in our preliminary studies. While the participant is facing away from the walkway and distracted, a contaminant or slipping hazard applied over a 0.9×0.9 m targeted section of the walkway to induce an unexpected slip at heel strike during the next trial. In an effort to add variety to the LOB responses, three different contaminants or slipping hazards will be used including vegetable oil, soapy water, and a carpet mat on a polished vinyl floor.

Measure naturally-occurring LOB responses in the real-world:

- Participants will be briefed on how to wear and use the wearable sensors, and the investigator will give the sensors to the participants for them to wear over the subsequent three weeks (no balance training participants) or two weeks (TT, NT, and ST participants) during their daily lives. Participants will be asked to wear the sensors for at least 10 hours a day.

21-1072 Validation and application of wearable sensors for capturing responses to losses of balance

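### Hypothesis 2: without a subject-by-environment term, the residual-spread test can mistake unequal event counts for a difference in variability, and the mean comparison can be miscalibrated

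*Combined protocol and SAP*

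**What the plan says.** Hypothesis 2, one of two hypotheses under the primary objective (Section 2.2), is that "Real-world LOB responses will show greater variety than laboratory-induced LOB responses". Section 5.2 tests it in two steps. First, "a repeated-measures ANOVA (with a random effect for subject) will first be used to compare means of key kinematic measures" between real-world and laboratory events. Second, variability is compared by "examining the model residuals between real-world and lab environments using hypothesis testing (essentially Levene's test) and interval estimation".

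Subject is the only random effect named. The section does not mention a subject-by-environment effect or a residual variance for each environment. It does not say whether residuals are conditional (after subtracting the predicted subject effect) or marginal, or whether events enter singly or averaged per person.

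On numbers, Section 14.1 says "30 non-balance training participants will be recruited for our primary objective", that "no formal effect sizes could be determined", and that the figure rests partly on "the number of expected LOBs estimated from prior work", with no count given. Section 8.2 says that "three trip obstacle heights from prior tripping studies will be used including 5, 7.5, and 10 cm", and lists three slip hazards, but not how many trips and slips each person receives. Real-world events are whatever occurs in three weeks of wear (Section 5.1).

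**The concern.** A person's typical response may differ between laboratory and daily life, and by a different amount from one person to the next. Section 3.1 makes this plausible: it describes laboratory events as contrived and real-world events as more varied in cause and surroundings. A model with a subject effect alone has no term for such a shift, so the shift enters the residuals. The subject effect is estimated mostly from the setting with more events, so the other setting receives most of the inflation.

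Laboratory counts are set by the investigators and real-world counts by chance, so unequal counts are likely. The residual test could then report greater variety in one setting when event-to-event spread is the same in both. The mean comparison has a related problem: it treats a person's events within one setting as independent once the subject effect is removed. Both steps bear on a primary-objective conclusion.

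**Working it through.** **Figure to reproduce.** The plan gives no power, alpha or event count for Hypothesis 2, so there is none. I take two-sided 5%, which is 2.5% in each direction.

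**Inputs from the documents.** 30 participants; one random effect (subject); a Levene-type test on that model's residuals; 3 trip heights and 3 slip hazards.

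**Assumed inputs.** 6 laboratory events per person (3 + 3), with 2 as a sensitivity case; random real-world counts with means of 1 to 12; within-person variance 1 in both settings; subject variance 1 or 0.49; shift variance T in each setting. True spread is therefore identical in the two settings.

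**Where the shift goes.** Let s_L and s_R be one person's shifts, each with variance T, and n_L and n_R that person's event counts. Ignoring shrinkage, the fitted subject effect absorbs (n_L·s_L + n_R·s_R)/(n_L + n_R). The remainder in each setting's conditional residuals has variance:

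- real-world: 2T × [n_L/(n_L + n_R)]²
- laboratory: 2T × [n_R/(n_L + n_R)]²

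| n_L, n_R | Real-world | Laboratory |
|---|---|---|
| 6, 1.5 | 2T × 0.8² = 1.28T | 2T × 0.2² = 0.08T |
| 6, 3 | 2T × (6/9)² = 0.89T | 2T × (3/9)² = 0.22T |
| 6, 6 | 2T × 0.5² = 0.50T | 0.50T |
| 6, 12 | 2T × (6/18)² = 0.22T | 2T × (12/18)² = 0.89T |

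The sparser setting is inflated more; equal counts cancel the effect.

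**Simulated false finding that real-world is more variable** (conditional residuals, 6 laboratory events, nominal 2.5%; ranges cover runs of 200 to 1,500 replicates):

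| T | 1.5 real-world events | 3 real-world events |
|---|---|---|
| 0.25 | 11-13% | 7-11% |
| about 0.5 | 28-34% | 13.5-18% |
| 1 | 63-70% | 44-46% |

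Boundary cases:

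- T = 0: 2.0-3.1%.
- Exactly 6 real-world events: 0.2-2.5%.
- Mean of 12 real-world events: the error reverses. Laboratory is falsely called more variable in 5.7-82.5% for shift SDs of 0.3 to 1.0.
- 2 laboratory events: 4.2-4.7% at a mean of 1 real-world event for shift SDs of 0.5 and 0.7, with the direction reversing by a mean of 3.
- Marginal residuals, 1.5 events: 2.5%, 4.2% and 5.0% for T = 0.25, 0.5 and 1. Some two-sided inflation from clustering remains, up to about 20% at 3 events and T = 1.

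**Mean comparison** (event-level, 6 laboratory events, nominal 5%, real-world means of 1 to 12):

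| Shift SD | False-positive rate |
|---|---|
| 0 | 3.5-5.4% |
| 0.3 | 8.0-11.4% |
| 0.5 | 10.7-21.9% |
| 0.7 | 16.7-33.3% |
| 1.0 | 22.3-42.5% |

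This inflation occurs even with balanced counts. With no shift but a real-world SD 1.5 times the laboratory SD, the rate is 13.7%, 11.8%, 8.6%, 4.9% and 2.1% at means of 1, 2, 3, 6 and 12. If events are first averaged per person and setting and then compared by paired t, it is 3.8-6.1%.

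**The case against.** The strongest reply is that Section 5.2 does not state the model that fails. It names a subject effect but does not exclude other terms, and a single residual variance is inferred from the name of the method. A classical repeated-measures ANOVA on per-person averages tests environment against the subject-by-environment term, so its mean comparison is valid. With marginal residuals most of the directional error in the spread test disappears. All of this stands, and it limits the point. It does not remove it. Averages no longer carry the event-to-event variety that Hypothesis 2 is about, so an event-level model is the likelier basis for the residual step. The readings also give different answers, so the choice must be made before analysis.

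A reader might infer that unequal counts alone create a false result. They do not: person-by-setting shifts are needed too, and the documents give no figure for either. A reader might also infer that the plan is tilted toward confirming Hypothesis 2. The direction depends on which setting has fewer events, and that is unknown.

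A further objection is that a within-person variance ratio leaves out differences between people in daily life, which could count as variety. The planned subject effect is already meant to take out between-person differences, so the target does not change in kind, but the plan should state it.

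**Conclusion.** The concern holds as a specification gap that should be fixed. As written, the Hypothesis 2 spread test can find a difference in variability where there is none. Under the assumed 6 laboratory and 1.5 to 3 real-world events per person and T of 0.25 to 1, the false real-world finding is about 7-70% against 2.5%. This requires varying person-by-setting shifts, unequal counts and conditional residuals. The upper end needs a shift variance as large as the within-person variance, which nothing in the documents supports or rules out.

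It would go too far to say that the mean comparison is anti-conservative. It can be, at about 8-42% with shifts and 6 laboratory events. It is nominal without shifts and with equal variances, can be conservative when real-world events are both more numerous and more variable, and is valid on per-person, per-setting averages.

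**What to change.** For each measure, replace the two steps with one event-level mixed model: a fixed environment effect, random subject and subject-by-environment effects, and a separate residual variance for each environment. Test Hypothesis 2 as the real-world-to-laboratory ratio of residual variances, with a 95% interval and a subject-level bootstrap as a check on the likelihood-ratio test. Take the mean comparison from the same model. State that the estimand is within-person, event-to-event variability, and give the planned laboratory and expected real-world event counts per person.

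The cost is a few lines of text and standard software, with no new data. In null simulations the replacement rejected equal variances in about 2.5-8% and equal means in 3-8% of trials; the upper values are the reason for the bootstrap check.

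The real price is power when real-world events are few. With 6 laboratory events and T = 0.25, rough simulation estimates at 1.5 to 3 real-world events per person are 27-49% at a variance ratio of 1.5 and about 50-80% at a ratio of 2. At a ratio of 3 with only 0.5 events, power is about 45%. The planned test rejects more often, but that cannot be credited as power while its error rate is uncontrolled. The interval should therefore be the main result, with the p-value secondary.
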